STUDY TITLE: Oral Penicillin Challenge in the Pediatric Emergency Department

NCT number: NCT03404804

Document date: 1aug22 last continuing review approval

PRINCIPAL INVESTIGATOR: [name], DO, MS

STUDY TITLE: Oral Penicillin Challenge in the Pediatric Emergency Department

A. PURPOSE OF THE STUDY

The purpose of this study is to utilize a parent-reported penicillin allergy questionnaire in a pediatric emergency department (PED) and demonstrate that providers will administer, and families will be willing to receive an oral penicillin challenge in those children deemed to have non-allergic and low-risk symptoms of true penicillin allergy.

B. HYPOTHESES / SPECIFIC AIMS

Aim 1: Demonstrate that a low-risk group of children with reported penicillin allergy will complete an oral penicillin challenge during a pediatric emergency department visit.

Hypothesis 1a: Providers will administer an oral penicillin challenge in the PED to children identified as having non-allergic and low-risk allergy symptoms.

Hypothesis 1b: Children with non-allergic and low-risk allergy symptoms will complete an oral penicillin challenge in the PED.

Aim 2: Conduct follow-up one day after oral challenge for all children and seven days after oral challenge for patients discharged with a prescription antibiotic to determine if a delayed or T-Cell mediated reaction occurs after exposure to multiple doses of penicillin or any other antibiotic prescribed at discharge.

Hypothesis 2a: Next day contact will be possible for over 95% of children who complete an oral challenge to demonstrate the ability to evaluate symptoms after PED discharge.

Hypothesis 2b: Seven-day follow-up will be completed in at least 90% of children who are discharged on a penicillin or other antibiotic to demonstrate the ability to monitor for delayed or T-Cell mediated reaction following the administration of multiple doses of penicillin.

Aim 3: Examine health care outcomes and prescription-related costs associated with illness treatment plans in children who are de-labeled as penicillin allergic after an oral challenge.

Hypothesis 3a: Health care outcomes (allergic reactions, number of illnesses, antibiotics prescribed, and ER/Urgent Care/Primary care visits) will be similar between children de-labeled as penicillin allergic compared to the general population.

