Hypothesis 3b: Prescription-related costs associated with illness treatment plans will be significantly less in children de-labeled as penicillin allergic.

C. BACKGROUND, SIGNIFICANCE, AND RATIONALE

Children often present to the pediatric emergency department with a parent reported allergy to medications. Allergy to an antibiotic in the penicillin family (hereafter termed penicillin) is the most commonly reported medication allergy, reported in 5-20% of patients.¹⁻⁶ Since physicians and advanced practice providers (hereafter termed providers) rely on these patient/parent reported allergies when making treatment decisions, a large group of patients are denied first-line antibiotic therapy due to misunderstood or misdiagnosed penicillin allergy.⁷ As a consequence, patients are prescribed second or third line medications that are more expensive and not the antibiotic of choice for their bacterial infection.^{8,9} An example of the health risks associated with

reported penicillin allergy was highlighted by Macy et al who found that, “A penicillin “allergy” history, although often inaccurate, is not a benign finding at hospital admission. Subjects with a penicillin “allergy” history spend significantly more time in the hospital, are exposed to significantly more antibiotics associated with Clostridium difficile (C. diff) and Vancomycin-Resistant Enterococci (VRE) and are associated with increased hospital use.”⁹ Additionally it has been shown that de-labelling patients reported to have penicillin allergy can lead to decreased prescription costs with very low rates of subsequent adverse reactions.¹⁰ Specific to penicillin allergy, greater than 95% of patients may actually tolerate a penicillin, either because they were never allergic or because they had an earlier allergy that subsequently resolved.¹¹

Our prior work utilized a novel structured penicillin allergy questionnaire in the PED and found that 76% of the children with penicillin allergy reported by families had exclusively low-risk allergy symptoms for true allergy (Table 1).¹² These symptoms were often adverse reactions, inconsistent with true allergy.¹³⁻¹⁵

Table 1: Categorization of Allergy Symptoms

Low Risk Group		High Risk Group	
Non-Allergic Symptoms	Low-Risk Symptoms	High-Risk Symptoms	
Runny nose	Rash	Facial swelling	Seizures
Diarrhea	Itching	Difficulty breathing	Rash*
Headache	Dizziness	Lip swelling	Itching*
Vomiting with med administration	Vomiting	Wheezing	Vomiting**

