Objective

Our primary objective is to demonstrate the feasibility of utilizing a novel penicillin allergy questionnaire in the PED to identify a low-risk group of patients who will complete an oral challenge in the PED to test for an IgE-mediated allergic reaction. This project will begin as a single site feasibility study, however including up to 2 other collaborative sites for enrollment has been favorably discussed. We do not anticipate this to be a single IRB scenario and will submit a timely comprehensive amendment if plans become concrete and the initial data here proves reliable.

Our secondary objective is to examine whether health care outcomes and prescription-related costs are comparable between children who are de-labeled as penicillin allergic after an oral challenge compared to a standard of care group who are not challenged in the PED.

Aim 1: Demonstrate that a low-risk group of children with reported penicillin allergy will complete an oral penicillin challenge during a pediatric emergency department visit.

Design/setting:

This will be a prospective study of children (2-16) presenting to the PED at the Children's Hospital of Wisconsin with a child or parent reported allergy to penicillin.

Population:

[figure not shown]
Inclusion Criteria: Children aged 2-16 with a parent/guardian (hereafter termed parent) reported history of allergy to a penicillin antibiotic in which the reported allergic reaction occurred at least twelve months prior to the current PED visit.

Exclusion Criteria: Children will be excluded:

- If they have a history of severe developmental delay or inability to communicate the effects of an allergic reaction (non-verbal). ED care team discretion can be utilized to determine ability to proceed with study with regards to developmental delay.
- History of a severe allergic reaction to skin tests
- Anaphylaxis in the past six weeks
- Current pregnancy
- Child is currently on a beta blocker medication
- Children who present to the PED with a rash
- Children who present with multiple episodes of vomiting on day of presentation
- Children presenting to the ED for asthma exacerbation
- Patients deemed too acutely ill for participation as deemed by the ED patient care team
- Non-English speaking families
- Wards of the state, in foster care or police custody or detention will be excluded.

Study Procedure (Figure 1):

Figure 1: Study Procedures for Full Protocol

¹Red boxes indicate oral-challenge-only study procedures

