
Design/setting and study population:

This study will include all children from Aim 1 who underwent an oral challenge in the PED after being determined to have low-risk symptoms on the allergy questionnaire.

Study Procedure (Figure 1, Aim 2)

- 1) A follow-up phone call will be made to all families whose child received an oral challenge.
- 2) If a family receives a one-time dose of antibiotic but does not receive a prescription for a penicillin antibiotic then they will be called on day 1 by a research team member who will administer a 5-minute allergy questionnaire that will review any possible symptoms of allergic reaction following the ED visit.
- 3) If a family receives a penicillin antibiotic prescription following the oral challenge, then they will be called on days 1 and 7 by a research team member for a 5-minute allergy questionnaire that will review any possible symptoms of allergic reaction following the ED visit.
- 4) The patient's primary medical provider will also be notified of the oral challenge results for both groups of patients via fax within 7 days of the oral challenge date.

Aim 3: Examine health care outcomes and prescription-related costs associated with illness treatment plans in children who are de-labeled as penicillin allergic after an oral challenge.**Design/setting and study population:**

This study will include children identified as having low-risk symptoms of allergy from Aim 1 who underwent an oral challenge (Group 1), and those who did not undergo an oral challenge in the PED (Group 2).

Study Procedure (Figure 1, Aim 3)

- 1) A follow-up 5-minute phone survey will be completed by research staff to the family. This follow-up will occur after their initial PED visit at 6 and 12 months.
- 2) The follow-up survey will include questions on health care outcomes since the PED visit that include but are not limited to: the number and type of diagnosed infections, number and type of antibiotics given, and allergic reaction history.

E. TOTAL NUMBER OF HUMAN RESEARCH PARTICIPANTS PROPOSED FOR THIS STUDY AT THIS SITE AND GLOBALLY. WHAT ARE THESE NUMBERS BASED ON?

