Descriptive characteristics will also be used to summarize the baseline patient characteristics and follow-up questionnaire responses for months 6 and 12 of the children who underwent the oral challenge in Aim 1. We will then conduct a three-level economic cost savings analysis. First, in order to calculate the potential cost savings if amoxicillin is filled for all penicillin allergic de-labelled patients, the median retail price of each non-penicillin antibiotic filled will be compared to the median retail price of amoxicillin. Second, we will calculate the cost avoidance savings assuming that patients who fill any amoxicillin/penicillin prescriptions would have filled cefdinir in its place. Lastly, we will extrapolate the total cost savings potentially generated by the approximately 6,700 patients per year treated in our PED who report penicillin allergy.

Sample Size Justification/Power Analysis:

We have determined that we need 50 patients to complete the oral challenge for the feasibility study to be complete. We will consent for questionnaire-screening approximately 250 children to achieve that number. This number is based off of our previous study; during that study 50 patients were approached per month for survey participation, 80% (40) agreed to participation, and 25% (10) of patients were found have high-risk symptoms of allergy and thus were found to be ineligible. Assuming that 50% of patients with low-risk symptoms will have either provider/family refusal to oral challenge this will leave approximately 15 patients per month to complete an oral challenge. Of the 50 children who complete the oral challenge, we estimate that 40 patients will receive a one-time oral challenge and 10 patients will receive an oral challenge and be sent home with a prescription. This estimation is based off of our previous study where approximately 20% of children who were eligible and willing to be tested were discharged home with a prescription antibiotic. If we are able to reach our enrollment goal prior to approaching 500 patients, we will end the feasibility study.

P. FINANCIAL RELATIONSHIPS

The study is funded with internal funds from the section of Pediatric Emergency Medicine and a grant from the Children's Research Institute which support the costs of accomplishing the oral challenges and other associated project costs.

Q. ADVERTISEMENTS / FLIERS

N/A

R. BIBLIOGRAPHY (*list pertinent literature references*)

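### The secondary objective asks whether prescription costs are comparable, Hypothesis 3b predicts they are lower, and the Section O cost analysis compares no groups, so it can support neither

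*Combined protocol and SAP*

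**What the plan says.** Three parts of the combined protocol and SAP bear on prescription costs.

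- **Section D, Objective.** The secondary objective reads: "examine whether health care outcomes and prescription-related costs are comparable between children who are de-labeled as penicillin allergic after an oral challenge". The comparator given there is unchallenged children receiving standard care. Health care outcomes and costs sit under the same word, and no margin is given.
- **Section B, Aim 3.** The hypotheses treat the two separately. Hypothesis 3a says that health care outcomes "will be similar between children de-labeled as penicillin allergic compared to the general population"; it does not cover costs. Hypothesis 3b does: "Prescription-related costs associated with illness treatment plans will be significantly less in children de-labeled as penicillin allergic". It names no comparator.
- **Section D, Aim 3, and Section O, Data Analysis.** Aim 3 takes low-risk children "who underwent an oral challenge (Group 1), and those who did not undergo an oral challenge in the PED (Group 2"). Both 6- and 12-month surveys ask about antibiotics received. Section O, however, plans to summarise the "follow-up questionnaire responses for months 6 and 12 of the children who underwent the oral challenge in Aim 1", and Group 2 does not appear. It continues: "We will then conduct a three-level economic cost savings analysis". At the first level, "the median retail price of each non-penicillin antibiotic filled will be compared to the median retail price of amoxicillin". The second level assumes that each amoxicillin or penicillin fill replaced a cefdinir fill. The third scales the savings up to about 6,700 patients a year.

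**The concern.** One quantity, prescription cost in de-labeled children, carries two different target statements. Finding it comparable and finding it significantly lower are different conclusions that need different evidence: an equivalence margin for one, a directional comparison for the other. The plan supplies neither and does not say which statement governs.

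The planned analysis does not settle the matter. Both statements concern how de-labeled children compare with other children, and Section O compares drug prices. What can be claimed about cost is therefore left open until the data are in. At stake is the cost half of the secondary objective, which also carries part of the protocol's rationale: Sections C and K both argue that de-labeling saves money.

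**Working it through.** **1. The statements side by side**

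| Place | Quantity | Direction | Comparator | Criterion |
|---|---|---|---|---|
| Section D, secondary objective | Outcomes and costs | Comparable | Standard of care, unchallenged | None |
| Section B, Hypothesis 3a | Outcomes | Similar | General population | None |
| Section B, Hypothesis 3b | Costs | Significantly less | Not named | None |
| Section O, cost analysis | Modelled savings, challenged children | Savings | None observed | None |

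The Section B hypotheses already split outcomes from costs. The secondary objective merges them, and that is where the conflict arises.

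**2. What the Section O cost analysis can produce**

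Let P denote a median retail price.

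- Level 1, over non-penicillin fills j in challenged children: saving = Σ n_j × (P_j − P_amoxicillin).
- Level 2, over n amoxicillin or penicillin fills: saving = n × (P_cefdinir − P_filled). The sign is set by the price list and the assumed substitution.
- Level 3: levels 1 and 2 scaled to about 6,700 patients a year.

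No term holds an observed cost from Group 2. None of the levels yields a between-group difference, an interval or a test, so the output bears on neither comparability nor a significant reduction.

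**3. Is there a stated figure to reproduce?**

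Not for costs: the documents give no alpha, sidedness, power, standard deviation, margin or Group 2 size. The accrual text does give a guide to Group 2. Of 50 approached per month, 50 × 0.80 = 40 agree; 40 × 0.75 = 30 are low-risk; 30 × 0.50 = 15 complete the challenge. This matches the stated 15 per month. The other 15 low-risk children are not challenged, so a Group 2 about as large as Group 1 is a reasonable assumption if those families can be followed.

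**4. What a real comparison could show**

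Assumptions, not in the documents: equal groups, a normal approximation for mean cost, differences in SD units, two-sided 5% for the interval and 5% for each one-sided equivalence test. Group sizes of 50 (Section O), 100 (Section E, one site) and 300 (Section E, three sites) are used.

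- Standard error = √(2/n). At n = 50 this is 0.20.
- 95% half-width = 1.96 × √(2/n).
- Detectable difference at 80% power = (1.960 + 0.842) × √(2/n). At n = 50, 2.802 × 0.20 = 0.56.
- Equivalence power, true difference zero = 2Φ(margin/SE − 1.645) − 1, or zero if negative. At n = 50 and margin 0.5, 2Φ(2.5 − 1.645) − 1 = 0.61. At margin 0.3, 0.3/0.20 = 1.5 is below 1.645, so power is zero.

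| n per group | 95% half-width (SD) | Detectable at 80% (SD) | Equivalence power, margin 0.3 SD | Margin 0.5 SD |
|---|---|---|---|---|
| 50 | 0.39 | 0.56 | 0% | 61% |
| 100 | 0.28 | 0.40 | 37% | 94% |
| 300 | 0.16 | 0.23 | 96% | about 100% |

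At 50 per group, a non-significant cost difference would say little about comparability. The fix therefore has to state how a null is to be read.

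**The case against.** The strongest reply is that the secondary objective is worded as a question. One may examine whether costs are comparable and answer no, and a saving would then answer the objective and support 3b. That stands: the objective makes no prediction, and the mismatch looks like loose drafting that joined outcomes to costs.

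A reader might go further and infer that the cost question can hardly fail, because a null would satisfy the objective and a saving would satisfy 3b. Under a two-sided 5% test with equal true costs, that gives 0.95 + 0.025 = 97.5%. The documents do not support this. No rule counts a non-significant result as comparable, no cost test or alpha is stated, and the planned analysis cannot return a null. Even under such a rule, significantly higher costs would contradict both statements.

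It can also be said that Section O shows the intended direction, since every level is framed as savings. That is fair, and it is a reason to resolve the conflict in favour of 3b. It does not make the modelled savings a test of 3b.

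Finally, this is a secondary objective in a feasibility study whose size was not chosen for costs. That limits the weight of the point.

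**Conclusion.** The point holds as an unreconciled conflict between the secondary objective and Hypothesis 3b, together with a cost analysis that can answer neither. It rests on the text alone and needs no assumption about the data. No false-positive or success probability belongs to it. The precision figures are conditional on assumed equal groups and SD units, and serve only to show why a null must not be read as comparability at feasibility size.

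The effect is confined to what may be claimed about costs. The feasibility aims and the safety follow-up are untouched. It should be corrected, because the plan as written leaves the cost claim undefined.

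**What to change.** **Section D, Objective.** Limit comparability to health care outcomes, and state the cost objective in the direction of Hypothesis 3b, with Group 2 as the named comparator.

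**Section O, Data Analysis.**

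- Include Group 2 in the month 6 and 12 summaries.
- Define cost per child from the antibiotics reported at those surveys and the median retail prices already planned.
- Report the Group 1 minus Group 2 difference with a 95% interval.
- State that 3b is supported only if the interval lies wholly below zero, and that an interval including zero is inconclusive and is not reported as comparable.
- Keep the three-level savings model as a separate, descriptive projection.

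**Alternative.** If no group comparison is wanted, call the cost analysis descriptive and remove both the significance claim in 3b and the comparability claim for costs.

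**Cost.** The first option needs some added analysis and a per-child cost definition. The comparison is non-randomised and, at 50 per group, imprecise. Permission for later contact is described within the Oral Challenge consent (Section D, Aim 1 procedures; Section N), so the sponsor should check that Group 2 families are covered. A null cost result could no longer be presented as meeting the objective. The alternative costs only wording, but gives up the cost claim.

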- 9) If there is a serious or anaphylactic reaction, emergency medicine will be given right away. The medicine is called epinephrine and comes in an Epi-Pen. Additional medications that could also be given include steroids, Benadryl, Zantac, and IV fluids. If a reaction occurs that requires emergency medicine the patient or the patient’s insurance are liable for the cost of this continued treatment. Their liability also includes any copay that may associated with the use of their insurance or if insurance does not cover the inpatient hospitalization. The potential costs for treating a reaction in which a patient is hospitalized may be thousands of dollars. However, we believe the risk of this occurrence to be very low as the incidence of true IgE mediated penicillin allergy is estimated to be in the range of 0.004% to 0.015%.^{21,22} Additionally, those children deemed low-risk on our questionnaire, likely never had an IgE mediated allergic reaction to begin with and are most likely falsely labeled as penicillin allergic. Families are also notified in the Oral Challenge consent and assent to call 9-1-1 and seek immediate medical attention if any serious reaction occurs after their child leaves the ED.
- 10) At the end of the visit the diagnosis will be recorded, and treatment/discharge will continue at the discretion of the PED physician/nurse practitioner/physician assistant . All patients who receive an oral challenge will be given an Allergy Oral Challenge Information sheet.
- 11) If a child is negative after oral challenge and has no need for an antibiotic at the time of discharge, the child will be discharged home.
- 12) If a child is negative after oral challenge and treatment would indicate a penicillin antibiotic, the child will be discharged home with a penicillin antibiotic.
- 13) Family contact information will be obtained in the questionnaire and utilized to complete follow-up phone calls after PED oral challenge.
- 14) The patient’s PMD (primary medical doctor) and pharmacy of record will be notified of the testing and results via fax within 7 days. Fax confirmations will be kept by the study team in the patient’s research file.

Aim 2: Conduct follow-up one day after oral challenge for all children and seven days after oral challenge for patients discharged with a prescription antibiotic to determine if a delayed or T-Cell mediated reaction occurs after exposure to multiple doses of penicillin or any other antibiotic prescribed at discharge.

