We have determined that we need 100 low-risk patients to complete the oral challenge at each of the three sites participating including here at Children's Hospital of Wisconsin. We will consent for questionnaire-screening approximately 500 children to achieve that number. This number is based off of our previous study; during that study 50 patients were approached per month for survey participation, 80% (40) agreed to participation, and 25% (10) of patients were found to have high-risk symptoms of allergy and thus were found to be ineligible. If 50% of patients with low-risk symptoms will have either provider/family refusal to oral challenge this will leave approximately 15 patients per month to complete an oral challenge and complete this portion of the study in approximately 7 months.

F. DRUGS OR PROCEDURES

Patient's family or guardian will be asked to answer an allergy symptom questionnaire that will be administered via an iPad. Patient's charts who are between the ages of 2-16 whose family has indicated an interest in allergy oral challenge will be reviewed.

If a child is eligible as defined in the questionnaire for allergy oral challenge and the family completes the challenge, then a gift card in the amount of \$50 will be provided for their time.

If a family completes all the telephone follow-up questionnaires at 6 and 12 months they will be mailed a \$25 gift card at the conclusion of each of the follow-up calls. (total of \$50 in follow-up stipends for full participation over one year.)

The allergy challenge consists of an oral amoxicillin challenge in the PED. A nurse will administer the oral challenge and will also be present during the process all of which will occur in the PED.

A follow up telephone survey monitoring for any adverse side effects/allergic reactions will be completed within 24 hours of the allergy oral challenge. If a patient receives a prescription for a penicillin or any other antibiotic then a follow up call will be made to monitor for any adverse side effects/allergic reactions at 7 days as well. Patients will also receive discharge instructions relevant to the study with phone numbers to call with questions.

A follow-up 5-minute phone survey will be completed by research staff to families of groups after their initial PED visit at 6 and 12 months. PI will review these results monthly or as relevant (notified by the study team) to monitor the long-term outcomes and safety of the protocol.

G. RISK CATEGORY:

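### The Aim 2 call steps give no day-7 call to children discharged on a non-penicillin antibiotic, although Hypothesis 2b counts them in its 90% target

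*Combined protocol and SAP*

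**What the plan says.** Four statements set day-7 follow-up for any antibiotic prescribed at discharge:

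- The Aim 2 statement (Section B, repeated in Section D) plans contact "seven days after oral challenge for patients discharged with a prescription antibiotic", without restricting the class. The exposure of interest is "penicillin or any other antibiotic prescribed at discharge".
- Hypothesis 2b (Section B) sets the target: "Seven-day follow-up will be completed in at least 90% of children who are discharged on a penicillin or other antibiotic".
- Section F gives the same trigger as a procedure: "If a patient receives a prescription for a penicillin or any other antibiotic then a follow up call will be made", at 7 days.

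The Aim 2 Study Procedure in Section D is narrower:

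- Step 1 is general and names no day: "A follow-up phone call will be made to all families whose child received an oral challenge".
- Step 2 concerns a family whose child has a one-time dose "but does not receive a prescription for a penicillin antibiotic then they will be called on day 1 by a research team member".
- Step 3 reads: "If a family receives a penicillin antibiotic prescription following the oral challenge, then they will be called on days 1 and 7".

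Section O expects 10 of 50 challenge completers to leave with a prescription and 40 to have only the one-time challenge. It will report the percentage lost to follow-up, and the frequency of delayed reactions with a 95% confidence interval.

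**The concern.** A child who completes the challenge and goes home on a non-penicillin antibiotic belongs to the Hypothesis 2b denominator, but the Aim 2 steps never schedule the contact that would count that child as followed up.

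This could distort the result in two ways. Completion could fall below 90% because of the call rule and not because families were unreachable, which is what the hypothesis is meant to measure. Or the denominator could shrink in practice to penicillin users, so that the reported percentage answers a narrower question than the one stated. Section O does not say whether a child with no scheduled day-7 call counts as lost to follow-up, so the report may not show which of these happened. Delayed reactions would also go unasked at day 7 in children whom Aim 2 expressly includes.

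**Working it through.** **Which children the steps leave out.** Step 2 can be read in two ways.

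1. Literally, it covers every family without a penicillin prescription. A child on another antibiotic then gets a day-1 call only.
2. Narrowly, it covers only children with no discharge course, in line with Section O's split into 40 one-time challenges and 10 with a prescription. A child on another antibiotic is then covered by neither step 2 nor step 3.

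Neither reading yields a day-7 call, and step 1 does not supply one because it names no day.

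**Whether such children can exist.** In the Aim 1 procedure, step 11 deals with challenge-negative children who need no antibiotic, and step 12 with challenge-negative children for whom a penicillin is indicated. Neither deals with a positive challenge or with treatment by another antibiotic. Step 10 leaves the rest open: "treatment/discharge will continue at the discretion of the PED physician/nurse practitioner/physician assistant". Aim 2, Hypothesis 2b and Section F each name other antibiotics. The group may be small, but the plan allows for it.

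**The plan's own figure.** Section O: 50 completers × 20% = 10 with a prescription, leaving 40 without. This reproduces. Applying the same 20% to Section E's 100 completers per site gives 20.

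**Highest completion possible under steps 2 and 3.** Let n be the number of discharge prescriptions and k the number that are non-penicillin. If those k children get no day-7 call, completion cannot exceed (n − k)/n.

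- n = 10: k = 1 gives 9/10 = 90%; k = 2 gives 8/10 = 80%.
- n = 20: k = 2 gives 18/20 = 90%; k = 3 gives 17/20 = 85%.

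The target of at least 90% therefore survives one such child in 10, or two in 20, and only if every scheduled call is completed.

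**Chance that the target is unreachable.** The documents do not give the non-penicillin share q. I assume 5%, 10% and 20%, treat prescriptions as independent, and assume that no such child is called on day 7. With k binomial:

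- n = 10: P(k ≥ 2) = 1 − (1 − q)^10 − 10q(1 − q)^9
- n = 20: P(k ≥ 3) = 1 − P(k = 0) − P(k = 1) − P(k = 2)

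| Assumed q | n = 10, P(k ≥ 2) | n = 20, P(k ≥ 3) |
|---|---|---|
| 0 | 0 | 0 |
| 5% | 0.086 | 0.075 |
| 10% | 0.264 | 0.323 |
| 20% | 0.624 | 0.794 |

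**The case against.** The best reply is that the plan already supplies the missing call. Section F is itself a procedures section and orders the 7-day call after any antibiotic, in agreement with Aim 2 and Hypothesis 2b. Step 3 does not say that only penicillin prescriptions qualify, and step 2 does not forbid a later call, so staff trained on the whole protocol can satisfy both. On the narrow reading of step 2, the steps are merely silent and Section F fills the gap. Figure 1, to which the Aim 2 procedure refers, is not shown and may set out the call groups correctly. The affected group may be close to empty, since the purpose of the challenge is to permit penicillin use. The larger probabilities rest on an assumed share and on Section F being disregarded for every such child. Hypothesis 2b carries no test, decision or stopping rule, its denominator is explicit, and discharge instructions and the 6- and 12-month surveys give some information on later reactions.

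Most of this stands as a limit on size. The loss is possible, not certain, and the probabilities only illustrate it. The conflict in the text remains: on its literal reading step 2 assigns these children a day-1 call, in the part of the protocol written specifically for Aim 2 follow-up. A correct Figure 1 would still leave that wording in place. Discharge instructions and surveys months later do not replace a day-7 contact, and they do not count towards Hypothesis 2b.

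**Conclusion.** The point holds and should be fixed. Steps 2 and 3 of the Aim 2 procedure provide the day-7 call for a narrower group than Aim 2, Hypothesis 2b and Section F require. That conclusion rests on the text alone.

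The size depends on what the plan does not state. If the steps are followed as written, two non-penicillin prescriptions among about 10, or three among about 20, make the 90% target unattainable. Over assumed shares of 5% to 20%, the chance of this runs from 9% to 62% with 10 prescriptions and from 8% to 79% with 20. There is no effect if the share is zero or if staff follow Section F. The primary feasibility objective is not affected. Figure 1 could not be checked.

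**What to change.** Reconcile steps 2 and 3 of the Aim 2 procedure with Aim 2, Hypothesis 2b and Section F, and check Figure 1 against the result, so that the children due a day-7 call and the Hypothesis 2b denominator are one set. For each child discharged on an antibiotic, record whether a day-7 call was due and whether it was completed, and report calls not scheduled apart from families not reached.

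As a secondary clarification, Section O could report delayed reactions up to day 7 over children with completed day-7 contact, separately from the day-1 results.

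The cost is wording in two steps and one tracking field. If the sponsor aligns the steps to any discharge antibiotic, the expected number of extra five-minute calls is n × q: 0.5, 1 and 2 with 10 prescriptions, or 1, 2 and 4 with 20, for assumed shares of 5%, 10% and 20%.
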